8.1.3 Serious Adverse Event

Serious Adverse Event

Adverse events are classified as serious or non-serious. A **serious adverse event** is any AE that is:

- fatal
- life-threatening
- requires or prolongs hospital stay
- results in persistent or significant disability or incapacity
- a congenital anomaly or birth defect
- an important medical event

Important medical events are those that may not be immediately life threatening, but are clearly of major clinical significance. They may jeopardize the subject, and may require intervention to prevent one of the other serious outcomes noted above. For example, drug overdose or abuse, a seizure that did not result in in-patient hospitalization, or intensive treatment of bronchospasm in an emergency department would typically be considered serious.

All adverse events that do not meet any of the criteria for serious should be regarded as **non-serious adverse events**.

8.1.4 Unanticipated Problems(UP) Involving Risk to Subjects or Others

Any incident, experience, or outcome that meets all of the following criteria:

- Unexpected in nature, severity, or frequency (i.e. not described in study-related documents such as the IRB-approved protocol or consent form, the investigators brochure, etc)
- Related or possibly related to participation in the research (i.e. possibly related means there is a reasonable possibility that the incident experience, or outcome may have been caused by the procedures involved in the research)
- Suggests that the research places subjects or others at greater risk of harm (including physical, psychological, economic, or social harm).

8.1.5 Preexisting Condition

A preexisting condition is one that is present at the start of the study. A preexisting condition should be recorded as an adverse event if the frequency, intensity, or the character of the condition worsens during the study period.

8.1.6 General Physical Examination Findings

At screening, any clinically significant abnormality should be recorded as a preexisting condition. At the end of the study, any new clinically significant findings/abnormalities that meet the definition of an adverse event must also be recorded and documented as an adverse event.

8.1.7 Post-study Adverse Event

All unresolved adverse events considered probably or definitely related should be followed by the investigator until the events are resolved, the subject is lost to follow-up, or the adverse event is otherwise explained. At the last scheduled visit, the investigator should instruct each subject to report any subsequent event(s) that the subject, or the subject's personal physician, believes might reasonably be related to participation in this study.

8.1.8 Hospitalization, Prolonged Hospitalization or Surgery

Any adverse event that results in hospitalization or prolonged hospitalization should be documented and reported as a serious adverse event unless specifically instructed otherwise in this protocol. Any condition responsible for additional surgery should be documented as an adverse event if the condition meets the criteria for and adverse event.

Neither the condition, hospitalization, prolonged hospitalization, nor surgery are reported as an adverse event in the following circumstances:

- Hospitalization or prolonged hospitalization for diagnostic or elective surgical procedures for a preexisting condition. Surgery should **not** be reported as an outcome of an adverse event if the purpose of the surgery was elective or diagnostic and the outcome was uneventful.
- Hospitalization or prolonged hospitalization required to allow efficacy measurement for the study.
- Hospitalization or prolonged hospitalization for therapy of the target disease of the study, unless it is a worsening or increase in frequency of hospital admissions as judged by the clinical investigator.

8.2 Recording of Adverse Events

At each contact with the subject, the investigator will seek information on adverse events by specific questioning and, as appropriate, by examination. Information on all adverse events will be recorded immediately in the source document, and also in the appropriate adverse event case report form (CRF). All clearly related signs, symptoms, and clinically significant abnormal diagnostic procedures results should be recorded in the source document, though should be grouped under one diagnosis.

All adverse events occurring during the study period (consent through Visit 3 – 1 month follow up) will be recorded. The clinical course of each event will be followed until resolution, stabilization, or until it has been determined that the study intervention or participation is not the cause. Serious adverse events that are still ongoing at the end of the study period will be followed up to determine the final outcome. Any serious adverse event that occurs after the study period and is considered to be possibly related to the study intervention or study participation will be recorded and reported immediately.

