3.1.1 Screening Phase

Subjects will be recruited from the University of Pennsylvania's Electrophysiology department. Patients will first be pre-screened using the procedure schedule to identify those that are undergoing an initial AF ablation procedure and therefore may be potentially eligible for enrollment. Patients who have met guideline recommendations for first-time AF ablation procedure will be approached by an EP physician (co-investigators) or a member of the research team prior to the AF ablation procedure. All potentially eligible patients will first have signed an informed consent for the clinical procedure by the appropriate clinical staff. We will follow applicable University of Pennsylvania regulations and Pennsylvania law pertaining to consent process and obtaining signatures. Written informed consent

for the research study (use of EnsoETM + EGDs) will be obtained the morning of the clinical procedure prior to any research procedures taking place.

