5.5 Blinding

Due to the nature of this study, the physicians will not be blinded to the randomization assignment, however participants will be blinded. Once a subject is randomized, the research team will receive the randomization assignment (EnsoETM or SOC) and proceed with the procedures per the assignment. In addition, the gastroenterologist interpreting the EGD study for the primary endpoint assessment will be blinded to the participants' randomization.

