7.3.3 Interim Safety Analysis

All subjects entered into the study and randomized at the baseline visit will have detailed information collected on adverse events for the overall study safety analysis. An interim safety analysis will be performed after the first 10

subjects are enrolled in the trial. At this time the safety and tolerability of the study device and research EGD procedure will be assessed and if, deemed safe and appropriate, enrollment will continue up to 70 subjects.

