11.1 Risks

Risks of the ablation procedure will be explained using the clinical procedure consent.

Additional risks of the study procedures are described below:

EnsoETM device risks: Placement of the EnsoETM device, similar to any device in the esophagus, can result in or exacerbate esophageal tissue damage, particularly in patients with known esophageal deformity or evidence of esophageal trauma. We believe these risks are similar to those whom receive the standard of care temperature monitor probes inserted into the esophagus during routine clinical procedures.

EGD procedure risks: Diagnostic upper endoscopy procedures are considered very safe and rarely can result in complications including bleeding, infection, and/or perforation. Large studies have reported the occurrence of any adverse event anywhere from 1 in 200 to 1 in 10,000 patients with major complications or death extraordinarily rare⁸.

Loss of Confidentiality Risks: there is the potential for loss of confidentiality during data collection.

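### After Visit 3 a new serious adverse event is recorded only if a team that knows the arm thinks it possibly research-related, so late esophageal events can be captured differently in the two groups

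*Combined protocol and SAP*

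**What the plan says.** Section 8.2 sets two recording rules in sequence. The first is unconditional and the same in both groups: "All adverse events occurring during the study period (consent through Visit 3 – 1 month follow up) will be recorded". Section 8.4 ends the reporting period at the same visit, and section 3.1.3 gives that visit a window of Day 30 −14/+30, that is Day 16 to Day 60. The second rule governs what comes later and is conditional. What must then be recorded and reported is: "Any serious adverse event that occurs after the study period and is considered to be possibly related to the study intervention or study participation".

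Section 8.3 grades relatedness against the research procedures. Section 3.1.1 shows what those are: written consent "for the research study (use of EnsoETM + EGDs) will be obtained" separately from the consent for the clinical ablation. The ablation and the control temperature probe are standard of care. Section 11.1 says that placing the device "can result in or exacerbate esophageal tissue damage", and names perforation among the rare complications of the EGD, which all patients undergo. Section 5.5 says that "the physicians will not be blinded to the randomization assignment", and section 8.6 says the same of the study team.

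Sections 3.1.4 and 6.2.4 provide for record review at about 3, 6 and 12 months in both groups, with phone contact under 3.1.4 if visits are missed. Adverse events are not among the listed items, although they are at the 1-month visit (3.1.3).

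**The concern.** The protocol uses endoscopic injury as a surrogate for atrio-esophageal fistula (section 1.2), so late serious esophageal events are the outcome that the surrogate stands for. After Visit 3, whether such an event enters the study record depends on an attribution, and the possible attributions differ by group. A late perforation in Group A could be ascribed to the device, the EGD or the ablation, and the first two qualify it for recording. In Group B the device was not used, so the EGD is the only named research procedure to which it could be ascribed.

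The person deciding knows the group. Section 8.6 accepts limited blinding on the ground that the endpoints other than the EGD reading are objective or quantitative. A relatedness opinion that decides whether an event is recorded at all is neither. Section 7.3.3 says that randomized subjects "will have detailed information collected on adverse events for the overall study safety analysis", without saying how late events would be handled there. With 30 patients per group, one recorded or unrecorded event would stand out in any listing.

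**Working it through.** The plan gives no figure to reproduce on this point, so the check is a comparison of the rules followed by a sizing.

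**Routes to recording, before and after Visit 3**

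| | Group A | Group B |
|---|---|---|
| Through Visit 3 | all adverse events | all adverse events |
| After Visit 3: device | qualifies if judged possible | not used |
| After Visit 3: EGD | qualifies if judged possible | qualifies if judged possible |
| After Visit 3: study participation | undefined | undefined |
| After Visit 3: ablation or standard probe only | not covered | not covered |

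The groups differ in one row, the device. The instruction in section 8.1.7 that subjects report later events does not remove the difference, because it too is limited to events believed to be related to participation.

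**Expected control perforations at any time.** Inputs: 30 controls (3.1); injury rate 35% (7.2), with 18% and 45% as the other rates cited in 1.2; one third of injuries being ulcers (1.2 says two thirds of abnormalities were erythema; treating the rest as ulcers is an assumption); 1 perforation per 10 ulcers (1.2).

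- 30 × 0.35 × 1/3 × 1/10 = 0.35
- 30 × 0.18 × 1/3 × 1/10 = 0.18
- 30 × 0.45 × 1/3 × 1/10 = 0.45

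Cross-check against the cited endoscopy series: 5 perforations in more than 800 patients is at most 5/800 = 0.625%, and 30 × 0.00625 = 0.19. This agrees with the 18% line. The 35% line is about twice as high.

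**Share falling after Visit 3.** The documents give no timing. Assume 10% to 50%.

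- At 35% injury: 0.35 × 0.10 = 0.035 to 0.35 × 0.50 = 0.175
- At 18%: 0.018 to 0.09
- At 45%: 0.045 to 0.225

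**At the cited fistula incidence** of 0.02% to 0.11% (1.1): 30 × 0.0002 = 0.006 to 30 × 0.0011 = 0.033 at any time, before any late share is applied. The chance of at least one fistula among all 60 patients is 1 − (1 − 0.0002)^60 = 1.2% to 1 − (1 − 0.0011)^60 = 6.4%.

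**Bound on the artificial difference.** With equal true rates, full capture in A and none in B, the expected difference in recorded fistulas would be 0.006 to 0.033. If half of the control events were captured, it would be 0.003 to 0.017. Under one rule for both groups it is 0.

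**The case against.** The strongest case against the point is that the text does not exclude control events. The threshold is only possible relatedness, every control has a research EGD with perforation as a named risk, and study participation is undefined and applies to both groups. Conversely, a Group A event may be put down to the ablation and left out. Section 11.1 also states the belief that the device's risks resemble those of the standard probe. This stands. A reader might infer that the same event is always captured in A and missed in B, or that the trial would set about 12 months of capture against 1 month. The documents support neither: capture is decided case by case, and after Visit 3 both groups have conditional capture only.

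It is also fair that no late comparison between groups is specified, that section 3.2.3 sets the safety endpoint at 1 month, and that the primary endpoint is read at Days 0–2 by a blinded reader. Chart review and phone contact could bring a late event to light in either group. But no rule requires it to be recorded as an adverse event unless it passes the relatedness condition.

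A reader might extend the point to events that start before Visit 3, because section 8.2 lets follow-up run to resolution, to stabilization, or "until it has been determined that the study intervention or participation is not the cause". For serious events this is largely answered. Section 8.2 adds: "Serious adverse events that are still ongoing at the end of the study period will be followed up to determine the final outcome", with no relatedness condition, and section 8.5.1 requires all events to be followed until resolved or stable. What remains is a tension in wording.

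**Conclusion.** The point holds as a limited one. After Visit 3 the recording rule depends on an unblinded relatedness judgement that Group A can satisfy by two named routes and Group B mainly by one, so it can produce differential capture of late esophageal serious events. It does not follow that it will, and the documents do not support a claim that a planned harm comparison is biased.

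The size is small: about 0.04 to 0.18 expected late control perforations at 35% injury, resting on the assumed 10% to 50% late share and on treating the non-erythema third as ulcers. At the cited fistula incidence the figure is lower still. The 1-month safety endpoint is largely rather than wholly unaffected, because a Visit 3 held on Day 16 ends unconditional recording under 8.2 before one month. Section 6.4 covers part of that gap, through unscheduled cardiology or GI visits at the center up to Day 30.

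The change is still worth making: it is cheap, it concerns the events that the surrogate stands for, and section 7.2 expects the pilot to inform larger studies.

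**What to change.** In sections 8.2, 8.4 and 3.1.4, state that every esophageal serious adverse event and every death, ideally every serious adverse event, found at the 3-, 6- and 12-month chart review or phone contact is recorded in both groups regardless of relatedness. Add adverse events of this kind to the data items in 3.1.4 and 6.2.4. Use the relatedness judgement only to decide expedited reporting.

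For events that start before Visit 3, reconcile the third stop condition in 8.2 with 8.5.1. No further change is needed there.

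The cost is protocol wording and one CRF item at reviews already planned for both groups. The downside is a few more records, most of them probably unrelated to the device.

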8.3 Classification of Adverse Events

Severity

- **Grade 1: mild**; asymptomatic or mild symptoms; clinical or diagnostic observations only; intervention is not indicated.
- **Grade 2: moderate**; minimal, local, or noninvasive intervention is indicated; limiting to age-appropriate instrumental activities of daily living (ADL; instrumental ADL refers to preparing meals, shopping for groceries or clothes, using the telephone, managing money, etc).
- **Grade 3: severe** or medically significant but not immediately life threatening; hospitalization or prolongation of hospitalization is indicated; disabling; limiting to self-care ADL (self-care ADL refers to bathing, dressing and undressing, feeding self, using the toilet, taking medications, and not bedridden).
- **Grade 4: life-threatening** consequences; urgent intervention is indicated.
- **Grade 5: death** due to an AE.

Relatedness

- 1) **Definite**: the AE is clearly related to the research procedures
- 2) **Probably**: the AE is likely related to the research procedures
- 3) **Possible**: the AE may be related to the research procedures
- 4) **Unlikely**: the AE is doubtfully related to the research procedures
- 5) **Unrelated**: the AE is clearly not related to the research procedures

Expectedness

AEs must be assessed as to whether they were expected to occur or were unexpected, meaning not anticipated based on current knowledge found in the protocol, investigator brochure, product insert, or label.

Expected: an AE known to be associated with the intervention or condition under study.

OHRP defines an **unexpected AE** as any AE occurring in one or more subjects participating in a research protocol, the nature, severity, or frequency of which is **not** consistent with either:

- 1) the known or foreseeable risk of AEs associated with the procedures involved in the research that are described in a) the protocol-related documents, such as the IRB-approved research protocol, any applicable investigator brochure, and the current IRB-approved informed consent document, and b) other relevant sources of information, such as product labeling and package inserts; or
- 2) the expected natural progression of any underlying disease, disorder, or condition of the subject(s) experiencing the AE and the subject's predisposing risk factor profile for the AE.

8.4 Adverse Event Reporting Period

For this study period during which adverse events must be reported is defined as the period from the initiation of any study procedures (consent) to the end of the study follow-up (1-Month follow up visit/Visit3). Adverse events that do not require expedited reporting (see section 9.5 below) will be reported in summary to the IRB at continuing review.

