3.1.3 Follow Up Visit (Day 30 -14/+30 days)

Follow up data will be collected at approximately 1 month following the ablation procedure. This is a standard of care follow up visits that typically occurs following an atrial fibrillation ablation procedure. The standard of care procedures that will be done at these visits include:

- Physical Exam
- Interim History and concomitant medication use
- Vital signs

In addition to the standard of care procedures, the research team will also collect the following:

- Adverse event information
- Atrial fibrillation recurrence

If a participant does not attend their routine 1 month clinical follow up, the research staff will attempt to contact the participant by phone to review their interim history, medication use and collect adverse event and atrial fibrillation recurrence information.

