3.2.3 Primary Safety Endpoints

All patients will undergo EGD following the procedure to evaluate the primary endpoint of esophageal thermal injury. We will also collect adverse events for all participants for 1 month following the ablation procedure.

4 Study Population and Duration of Participation

All patients will have met guideline recommendations for the AF ablation procedure and will have signed an informed consent for the clinical procedure.

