4.4 Duration of Study Participation

Participants will be involved for approximately 13 months including screening and follow-up. After consent, their active participation in the intervention phase will last up to 3 days to complete the ablation procedure and EGD testing. The follow up for safety evaluation will occur approximately 1-month post-ablation during the routine clinical follow up visit. Additional data will be collected via chart review for 1-year post-ablation from routine clinical follow up care post ablation which occurs at approximately 3, 6 and 12 months.

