5.6 Device Accountability

Device accountability logs will be kept on file, will be completed on a regular basis, and will include product number, date of use, participant ID code, device damaged/destroyed and date of damage/destruction (including return date to Attune).

6 Schedule of Study Visits, Procedures, and Data Extraction

Study Phase	Randomization/ Intervention Phase		Follow up Visit
	1	2	3
Study Days	Day 0	Day 0-2	Day 30 -14/+30 days
Research & Clinical Procedures			
Informed Consent	X		
Review Inclusion/Exclusion Criteria	X		
Randomization	X		
Ablation procedure (with temperature monitoring or EnsoETM device)	X		
Overnight monitoring post ablation	X		
EGD (Esophagogastroduodenoscopy)		X	
Discharge (1-2 days post ablation)		X	
Adverse Event / Unanticipated Problems Assessment	X	X	X
Data collection			
Demographics	X		
Medical History/Interim History*	X	X	X
Physical Examination*	X	X	X
NYHA	X		
Vital Signs: BP, HR, RR*	X	X	X
Height and Weight	X		
Pregnancy Test	X		
Clinical Laboratory Evaluation	X	X	
Clinical Imaging	X		
Prior/Concomitant Medications	X		X

* Interim medical history, physical exam, and vitals will be collected via chart review from routine clinical care follow up post-ablation visits that occur at approximately 3, 6 and 12 months. If a participant does not attend their follow up visits, the research staff will attempt to contact the participant by phone to review their interim history, medication use and collect atrial fibrillation recurrence information.

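### AE collection ends at Visit 3, which may fall anywhere from Day 16 to Day 60, so early attenders can have less than the one month stated in 3.2.3

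*Combined protocol and SAP*

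**What the plan says.** All references are to the combined protocol and SAP.

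- **Duration stated.** 3.2.3 (Primary Safety Endpoints): "We will also collect adverse events for all participants for 1 month following the ablation procedure".
- **Where the period ends.** 8.4 runs reporting from consent "to the end of the study follow-up (1-Month follow up visit/Visit3"). 8.2 agrees: "All adverse events occurring during the study period (consent through Visit 3" at 1 month). Both tie the end to a visit, not to a fixed day.
- **When that visit may occur.** The heading of 3.1.3 reads "Follow Up Visit (Day 30 -14/+30 days"), and the section 6 schedule repeats "Day 30 -14/+30 days".
- **How the timing is described elsewhere.** 4.4: "The follow up for safety evaluation will occur approximately 1-month post-ablation during the routine clinical follow up visit".
- **Who gets a contact near Day 30.** 3.1.3: "If a participant does not attend their routine 1 month clinical follow up, the research staff will attempt to contact the participant by phone", and AE information is among the items to be collected. 6.2.3 says the same for those who do not return. 6.5 and 6.5.1 attempt an AE contact at about 30 days for participants who withdraw before the 30-day visit.
- **What reaches past an early Visit 3.** 6.4 assesses AEs at unscheduled visits to the site's Cardiology or GI practice through 30 days. 8.2 asks about AEs at each contact and covers "Any serious adverse event that occurs after the study period and is considered to be possibly related to the study intervention" or participation. 8.1.7 has participants report later events believed related. 8.5 requires expedited reporting of SAEs once known. 3.1.4 reviews charts at about 3, 6 and 12 months and attempts calls after missed visits.

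**The concern.** Two rules set the length of AE collection. One is a duration, in 3.2.3; the other is an event, Visit 3, that can fall well before or well after that duration has passed. A participant who attends early and within the window leaves the defined period before one month is up, and nothing then requires the team to ask about AEs near Day 30.

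The protocol treats other participants differently. Someone who misses the visit, or who withdraws before it, is to be contacted about AEs at about one month. Someone who complies and is seen on Day 16 is not. That looks more like an oversight than a choice.

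At stake are the completeness of AE data and a common observation period. AE collection is one of the two parts of 3.2.3, the other being the EGD on Days 0 to 2. Section 7.3.3 plans an overall safety analysis using AEs from all randomized subjects, and the documents give no onset cut-off that would put participants on the same footing.

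**Working it through.** **Inputs**

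- Day 0 is the day of ablation (3.1.2).
- Visit 3 has target Day 30 and window -14/+30 days (3.1.3 and the section 6 schedule, which agree).
- The AE period ends at Visit 3 (8.2, 8.4).
- One month is taken as 30 days. This is an assumption, because 3.2.3 does not give days. It follows the protocol's own Day 30 target for the one-month visit and the 30-day horizon in 6.4 and 6.5.

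**Step 1: the window.** Earliest day = 30 - 14 = 16. Latest day = 30 + 30 = 60.

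**Step 2: shortfall against one month.** Shortfall = 30 - (day of Visit 3), for visits before Day 30.

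| Day of Visit 3 | Shortfall | Share of 30 days |
|---|---|---|
| 16 | 30 - 16 = 14 days | 14/30 = 46.7% |
| 29 | 30 - 29 = 1 day | 1/30 = 3.3% |
| 30 or later | none | 0% |

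**Step 3: sensitivity to the length of a month.** With 31 days, visits on Days 16 and 29 are 31 - 16 = 15 and 31 - 29 = 2 days short. With 28 days, a Day 16 visit is 28 - 16 = 12 days short and a Day 29 visit is not short. The conclusion does not turn on this choice.

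**Step 4: spread of the defined period.** After ablation it can last from 16 to 60 days, and 60/16 = 3.75. These are the window limits, not expected follow-up; the documents give no distribution of visit days.

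**Step 5: what is still captured after an early visit.**

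| Provision | What it reaches | Limit |
|---|---|---|
| 6.4 | AEs at unscheduled visits to Day 30 | Site Cardiology or GI practice only |
| 8.2, questioning | AEs asked about at each contact | Needs a contact; the commitment to record all AEs ends at Visit 3 |
| 8.2, later SAEs | SAEs after the period | Possibly related only |
| 8.1.7 | Participant self-report | Events believed related |
| 8.5 | Any SAE, no end date of its own | Must become known to the team |
| 3.1.4 | Chart review; calls after missed visits | Chart data where available; AEs not listed as an item |

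What is left without required capture is mainly non-serious AEs, and unrelated SAEs, that are seen elsewhere.

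**The case against.** The strongest reply is that the one month in 3.2.3 is simply the name of Visit 3. Sections 8.2, 8.4 and 6.2.3 all label that visit as the one-month visit, and 3.1.3, 4.4 and 6.2.3 describe its timing as approximate. On that reading 3.2.3 and 8.4 describe the same period, with an ordinary window around a standard-of-care visit. This is a fair reading and the documents do not exclude it. It removes the contradiction but not the unequal observation periods.

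A second reply is that other provisions cover the gap. They do so in part, and 6.4 is best seen as a backstop for early attenders, not as a further inconsistency. But each provision is conditional, and none requires the team to ask an early attender about AEs near Day 30.

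A third reply is that the consequence is slight: at most 14 days on a 30-day month, mainly for less serious or unrelated events, in an unknown and possibly zero number of participants. That stands and sets the severity.

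Three stronger readings are tempting. A reader might infer that AEs after an early visit go uncollected; the provisions tabulated above show otherwise. A reader might infer that the safety comparison between groups is biased; nothing suggests that visit timing differs by arm, and no between-arm test of AE rates is specified. A reader might infer that a wide window is itself an error; it is not. The difficulty lies only in using the visit as the end of AE collection when a duration is also stated.

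**Conclusion.** The point holds in a limited form. As written, a participant seen on Days 16 to 29 has a defined AE period 1 to 14 days short of 30, with no required later AE contact near Day 30, although non-attenders and withdrawn participants are to be contacted at about then. Whether this contradicts 3.2.3 depends on whether its one month is a duration or a label for Visit 3. On either reading, the safety summary can combine periods that differ up to 3.75-fold at the window limits.

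The day arithmetic is certain given a 30-day month. How many participants would be affected cannot be determined from the documents, so no total is claimed. The EGD endpoint is untouched. Severity: low end of minor.

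**What to change.** - In 8.2 and 8.4, end AE collection at Day 30 or Visit 3, whichever is later. Use matching wording in 3.1.3, 6.2.3 and the section 6 schedule.
- Extend the phone or final contact at about 30 days, already used for non-attenders and withdrawn participants, to anyone whose Visit 3 falls before Day 30: a short AE call on or just after that day.
- Summarise AEs by group with onset through Day 30, and list later-onset events separately. Confirm that the AE case report form records an onset date for every event. The form is not in the documents, so it may already do so; 8.5 asks for onset in expedited reports.

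The cost is wording in five places and one short call per early attender. No extra visit and no change in sample size is needed.
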